#### **Health Intervention Infrastructure**

The bundle of care during the intervention will include triage in the OPD using an additional custom Android web-app, running locally on the device with no required Internet connection. As with the data collection app, this application will be password protected and data will be stored encrypted on the device. Following each triage, the triage data will be sent to a local low-cost Unix server Soekris box based in a secure room at each site. Data will be sent through encrypted HTTPS requests to server-side PHP scripts, which insert it within MySQL tables.

The clinician dashboard that will be used to clinically manage all children in the OPD who have been triaged will be implemented as a password protected website accessible by registered medical staff on any computer or tablet on the local network. As with the triage app, this website runs completely locally, independent of an outside Internet connection and is not accessible from off-site. The dashboard is implemented using the Laravel (https://laravel.com), a PHP web framework, which queries the MySQL server tables securely. Personal identifiers will be collected in the triage app and sent to the server for display on the dashboard as is necessary for correct identification of patients, but such information will never leave the hospital site. As the study hospitals already have computers in their OPDs, use of the clinical dashboard will not be extra work for the hospital staff or interfere with other tasks.

# 17. Statistical Analysis

### **Model Development**

We will develop a logistic model that will predict severe infection and sepsis in children. Akaike's Information Criterion (AIC) will be used as a summary measure to select predictors for inclusion in the model. The final selection of a model will be judged on model parsimony, availability of the predictors (with respect to resources and cost), discrimination and calibration. Bootstrapping (with replacement) will be used for internal validation. Net Reclassification Index for external (Kenya) and geographical/high malaria prevalence (Jinja) will be used for validation of the prediction model. These cohorts will allow us to optimize and re-calibrate (if required) the prediction model. Appropriate triage risk threshold selected based on data, simulation and expert opinion. The final model will be integrated into an application for use on a mobile device and electronic dashboard.

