### Figure 1. Study Schema.

#### Updated Timeline due to COVID-19:

Phase:	Baseline	Training		Intervention	A	nalysis
Duration:	6 months	1 month		6 months	1	l months
Site 1: Kenya	Delayed	Delayed		Delayed	B	aseline data ollection
Site 2: Jinja	Baseline data collection	Model development, usability testin and training	ıg,	Routine use of PRST and continued data collection	St ar re R	tatistical nalysis and porting of esults
Control: Kenya Delayed					B co	aseline data
Additional Site: Gulu Uganda			Base	eline data collectio	n	Routine use of PRST

Phase I (6 months) will be a prospective observational cohort at Mbagathi County Hospital in Nairobi, Kenya, and Jinja Regional Referral Hospital in Jinja, Uganda. During this period, there will be no changes to healthcare delivery procedures in the study hospitals. Triage will continue to be performed by hospital staff using ETAT+ guidelines, the system that is currently in effect at the study hospitals [7]. Data collection will be undertaken in the triage waiting area. While participants are waiting for their turn to be seen by the **hospital triage nurses**, our trained **study nurses** will collect data on a pre-selected list of predictor variables (see Appendix A). These data will be used to develop a clinical prediction model based on the need for hospital admission.

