#### Changes due to the impact of COVID-19:

We anticipate that the weekly number of admissions will return to baseline over the next 2-3 months. Therefore, Phase I will be split into baseline data collation during a pandemic period (first 3 months), and non-pandemic period (latter 3 months)

**Control Site (Phase I, 12 months):** Kiambu County Referral Hospital in Nairobi, Kenya will serve as the control site and no intervention will be implemented. At this site, Phase I will commence for a period of 12 months. There will be no Phase II or Phase III.

Phase II (1-3 months) will involve technology development, usability testing, and training.

**Phase IIa: Technology Development.** A risk prediction model will be derived using the data collected in Phase I and implemented in a Digital Triaging Platform, along with a digitized version of the ETAT+ guidelines. The Digital Triaging Platform, including vital sign measurement devices (PhoneOx [10] and RRate [11]) and the mobile application and clinical dashboard [12][13][14] has already been developed and evaluated. Once the digital triage tool has been developed, it will be evaluated in potential users using simulated patient scenarios and a 'Think Aloud' method.

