### Changes due to COVID-19

The global COVID-19 has introduced many challenges to the successful completion of this project. We have been unable to initiate Phase I of the project in Nairobi, Kenya due to restrictions implemented to reduce the risk of spread of COVID-19. We have made good progress in recruitment in Jinja, Uganda. I consultation with our investigators, implementation partners and funders we have decided to add an additional site at Gulu Regional Hospital in Uganda. Gulu Regional Referral Hospital will serve as a control site while the intervention phase (Phase III) takes place at Jinja Regional Referral Hospital. Once the intervention period has been completed in Jinja, the intervention will be introduced at Gulu Regional Referral Hospital.

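### Section 17 labels Jinja a geographical validation cohort, but under the v5.0 timeline Jinja is the only derivation site, so an assessment there is internal or temporal validation

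*Combined protocol and SAP*

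**What the plan says.** Protocol v5.0, section 17 (Model Development), plans a new logistic model with bootstrap internal validation. It then says that the Net Reclassification Index "for external (Kenya) and geographical/high malaria prevalence (Jinja) will be used for validation of the prediction model". The same cohorts are to be used for optimising and, if needed, recalibrating the model. Integration of the final model into the application comes last. The section names no derivation cohort, states no held-out sample and does not mention Gulu.

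The derivation data are identified in section 7 (Trial Design):

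- Phase IIa: "A risk prediction model will be derived using the data collected in Phase I and implemented in a Digital Triaging Platform".
- Phase I: it "will be a prospective observational cohort at Mbagathi County Hospital in Nairobi, Kenya, and Jinja Regional Referral Hospital in Jinja, Uganda", and "These data will be used to develop a clinical prediction model based on the need for hospital admission".

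The COVID-19 changes alter which of those data exist, and when:

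- Section 8 (Changes due to COVID-19) reports for Kenya: "We have been unable to initiate Phase I of the project in Nairobi, Kenya due to restrictions". For Uganda it reports: "We have made good progress in recruitment in Jinja, Uganda".
- In the Updated Timeline in section 7, Jinja's row goes from baseline collection to "Model development, usability testin and training". Kenya is marked delayed until the final, analysis column.
- Section 8 adds Gulu as a control site for the period when Jinja is in Phase III.

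**The concern.** Geographical validation asks whether a model built in one place works in another. That needs a site that did not contribute to the fit. Under the v5.0 sequence Jinja is the site that builds the model, so its data cannot answer the question, however they are divided.

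At stake is what can be claimed about transportability. If section 17 is followed literally, same-site performance would be reported as evidence of geographical and high-malaria validity, and the tool would enter Phase III with that label. Meanwhile Gulu, the one independent cohort whose baseline is scheduled during the main study period, has no stated validation role.

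A second difficulty is that the cohorts named for validation are also to be used for recalibration. A model adjusted in a cohort and then assessed in that cohort has not been independently tested there.

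**Working it through.** **Step 1. Reproduce the plan's own figure.** Section 13 gives N = (n × 10)/I with n = 10 predictors and I = 12%. This is (10 × 10)/0.12 = 833.3, which matches the stated 833.

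**Step 2. Place each cohort on the v5.0 timeline** (section 7 Updated Timeline, section 8, section 17).

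| Cohort | Before model development | During Jinja Phase III | Analysis period | Validation role in section 17 |
|---|---|---|---|---|
| Jinja | Phase I baseline | Phase III, tool in use | No new collection shown | Geographical, high malaria |
| Kenya | None (delayed) | None (delayed) | Baseline | External |
| Gulu | None | Baseline, as control | Routine use of tool | None |

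The timeline table is partly broken in the text available, but the prose of section 8 confirms the Kenyan delay, the Jinja recruitment and Gulu's role.

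**Step 3. Count the data available at model development.** Section 13 gives a Phase I minimum of 1,000 and a COVID-19 increase of 250 per experimental site.

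- Jinja: 1,000 + 250 = 1,250 children; 0.12 × 1,250 = 150 admissions.
- Kenya: 0. Gulu: 0.
- Jinja share: 1,250/(1,250 + 0 + 0) = 100%.

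**Step 4. Classify every assessment that Jinja could supply.**

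- Same Phase I records, no correction: apparent performance.
- Bootstrap on Phase I: internal validation.
- A held-out part of Phase I: still internal validation.
- Phase III records: temporal validation, with the tool already in use, and too late for the pre-integration step in section 17.

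None is geographical validation.

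**Step 5. Check whether the delay created the problem.** It did not. The main text of section 7 already lists Jinja with Mbagathi as a Phase I site whose data develop the model. The delay makes Jinja the sole source and removes Kenyan data from the period before deployment.

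**Step 6. Illustrate the optimism if apparent performance were reported uncorrected.** This rests on assumptions that are not in the documents: independent normal predictors, ten of them with a true log-odds coefficient of 0.3, about 12% events, all candidates fitted without selection, and 60 repeats. The entries are the AUC on the fitting data minus the AUC on new data from the same population.

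| N | 10 candidates | 50 candidates |
|---|---|---|
| 833 | 0.030 | 0.124 |
| 1,000 | 0.026 | 0.116 |
| 1,250 | 0.017 | 0.092 |
| 4,000 | 0.004 | 0.029 |

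The range is 0.004 to 0.124, driven by candidate count and sample size. It measures overfitting only and says nothing about loss of performance at another site.

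**The case against.** The strongest reply is that section 17 never says the same Jinja children both fit and test the model. That is correct. A reader might infer that validation takes place on the training records. The inference is strong, because validation is placed before integration and only Jinja Phase I data exist then, but it is not stated text. The point does not depend on it, since step 4 shows that no division of Jinja data is geographical.

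Second, overfitting is not ignored. Section 17 plans bootstrapping. The COVID-19 analyses in the same section mention test sets spanning both pandemic periods, without giving site or split. The published protocol paper places model comparisons inside resampling. This stands: internal performance can be properly estimated. It does not supply a second site.

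Third, Kenya is delayed, not dropped. A reader might conclude that cross-site performance would have no support at all; the documents do not bear that out, because Kenyan baseline remains in the timeline and Kenya remains the named external cohort. The published paper's Discussion also says that performance may vary by location and disease prevalence. What is lost is external validation before Jinja Phase III.

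Fourth, Jinja might be meant to validate the Kenyan model described in section 5, which was built on over 1,000 children. That does not fit section 17, which sets out to develop a model, or Phase IIa, which derives it from Phase I.

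Finally, the published paper uses net reclassification only for optimisation and recalibration across sites and does not call Jinja a validation cohort. It predates v5.0 and has no Gulu, so it does not settle the roles.

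**Conclusion.** The point holds. The cohort roles in section 17 contradict the v5.0 sequence: at model development all the data come from Jinja, and no separate site is available for validation until after the tool is in use there. This is more than missing detail, because following the stated rule would attach a geographical label to same-site performance.

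The conclusion rests on the updated timeline being current and on section 17 stating no other derivation source. It needs no numerical magnitude. A reader might want to attach a single optimism or shrinkage figure; the documents do not support one, because they fix neither the number of candidate parameters entering selection nor the model's strength. The AUC range above is an illustration under declared assumptions, and it applies only if performance is reported without the planned bootstrap correction.

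**What to change.** Rewrite the Model Development text of section 17 to state:

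- Jinja Phase I is the derivation cohort, with bootstrap optimism-corrected internal validation. Any held-out part is declared and called internal; any use of Jinja Phase III data is called temporal.
- Gulu baseline, and Kenyan baseline when collected, are the external/geographical validation cohorts.
- In each external cohort the performance of the unmodified model is reported first. Recalibration in that cohort is a separate, later step and is not then presented as validation in the same data.
- No external validation precedes Jinja Phase III.

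The cost is a change of wording; all the data are already planned. The downside should be stated openly: external validation arrives only after deployment at Jinja, so it cannot fill the pre-integration step that section 17 now describes. Gulu tests transport to another site, but the documents give no malaria prevalence for it, so the contrast between malaria settings still depends on the delayed Kenyan data.

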#### **Outcomes Analysis**

We will compare the proportion of children at the two intervention sites receiving a completed bundle within 60 minutes to the historical and the contemporaneous control group (Marascuillo procedure). The median time to an appropriate bundle of care will be compared using a Mann–Whitney U test. The triage prioritization between the phases and the proportion of children who received and appropriate bundle of care within each triage categorization will be compared with Fisher's exact tests. Segmented regression analysis of the interrupted time series of the pre- and post- intervention periods will be used to assess immediate effects and effects over time, controlling for prior trends that may continue without our intervention. Quantile regression will be used to estimate the median differences. We will compare the estimated times at end of the intervention period with the expected counterfactual value, had the pre-intervention trend continued as if the intervention never occurred. We will compare the time to event (treatment bundle) using the Kaplan-Meier estimator with censure at 180 minutes. Secondary outcomes will be compared using generalized estimating equations.

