### 13. Sample Size

### **Model Development Considerations**

The sample size for model development is based on a sampling strategy that takes into account the number of predictor variables (either binary or continuous) to be used in a model which has been used in a similar study [13]. This accounts for a minimum standard of 10 events per effective variable and can be expressed mathematically as:  $N = [n \times 10]/I$ , which demonstrates the relationship between the number of predictor variables (n), the event rate (I), and the required sample size (N). Our previous experience that allowed for a minimum of 10 events per selected variable (admission rate of 12% and 10 predictors) would estimate a sample of at least 833 children. The sample size needed to detect a 20% increase in the proportion of children who receive the bundle of care within one hour was calculated using the stats package in R.

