### **Power to Detect Difference Considerations**

We have estimated the proportion of children who currently receive a bundle of care within one hour in the pre-intervention group to be 27%, based on findings from previous studies [19] and confirmed in our feasibility trial of the application and dashboard in Uganda. We will need at least 750 children for each of the pre-intervention and post-intervention conditions, using an alpha of .05, at power of 80%, to detect a 20% decrease in the proportion of children who receive the bundle of care within one hour.

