## Sampling and recruitment Sample size

**Model development considerations** The sample size for model development is based on two components: the number of predictors expected in the final model (effect-ive variables), n, and the outcome event rate, I. We employ the typical minimum standard of 10 events per effective variable and calculate the sample size as  $N = (n \ x \ 10)/I$ . Based on our previous study at a Kenyan hospital [16], we estimate the admission rate as I = 12%, and thus, to allow for a model with 10 predictors we require a minimum sample of 833 children.

**Power to detect difference considerations** Based on an assumed pre-intervention rate of 27% of children who receive a bundle of care within 1 h, an assumed 20% relative increase due to the intervention, and an alpha of 0.05, an estimate of 750 children per group is needed for 80% power. The assumed pre-intervention rate is consistent with previous studies [19] and confirmed in our feasibility trial of the application and dashboard in Uganda.

**Selected sample size** Based on the uncertainty commonly present in these smaller sample sizes [20], the desire to include the possibly of modelling non-linearities in our models (using machine learning methods) and the clinical feasibility (large case load) we plan to target a larger sample of 4000 at each site, with a minimum sample size of 1000 participants enrolled in Phase I. Based on the activity at our selected sites this would require no more than a 60% recruitment rate during a sixmonth period.

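### Version 5.0 tests the 60-minute proportion with an all-pairs procedure although it asks for only two contrasts; with three groups this wastes about 14–16% of the sample, which matters only if analysed numbers fall well below target

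*Combined protocol and SAP*

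**What the plan says.** Protocol version 5.0, section 17 (Outcomes Analysis), begins: "We will compare the proportion of children at the two intervention sites receiving a completed bundle within 60 minutes to the historical". The sentence goes on "to the historical and the contemporaneous control group (Marascuillo procedure"). It names two comparators for the intervention sites. It does not ask whether the two controls differ from each other, and it does not say how many groups enter the procedure.

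Section 13 (Power to Detect Difference Considerations) puts the proportion of children who now "receive a bundle of care within one hour in the pre-intervention group to be 27" per cent. It then sizes two groups: "We will need at least 750 children for each of the pre-intervention and post-intervention conditions". The setting is "using an alpha of .05, at power of 80%, to detect a 20% decrease in the proportion of children". There is no allowance for more than one comparison. The preceding subsection (Model Development Considerations) describes the same target in the opposite direction: "The sample size needed to detect a 20% increase in the proportion of children". The published protocol (Sample size) gives "an assumed 20% relative increase due to the intervention, and an alpha of 0.05".

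Section 13 (Selected Sample size) then sets a target of 4000 at each site, with at least 1000 in Phase I.

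**The concern.** Marascuilo's procedure gives simultaneous protection to all pairs among k groups. Its hurdle is the square root of the 95% point of chi-square on k − 1 degrees of freedom. With an intervention, a historical and a contemporaneous group there are three pairs, and one of them, control against control, is not a question the plan poses. The hurdle for the two wanted contrasts is therefore higher than 5% family-wise control over those two requires.

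The sizing assumes one contrast at z = 1.960, so the named test and the sample-size calculation do not match. At stake is power for the 60-minute comparison. Validity is not at stake: the procedure is conservative, so it neither inflates false positives nor biases the estimates.

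**Working it through.** **Inputs.** Baseline 0.27, alpha 0.05 and power 80% (section 13). Alternative 0.324, from the 20% relative increase in the published protocol; 0.216 if the decrease in section 13 is taken as relative. Assumptions: two-sided testing, k = 3, equal groups.

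**The plan's own figure.** With unpooled variance, n per group = (1.960 + 0.842)² × [p1(1 − p1) + p2(1 − p2)] / (p1 − p2)².

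- 0.27 vs 0.324: 7.849 × (0.1971 + 0.2190) / 0.002916 = 1120 (pooled variance: 1123).
- 0.27 vs 0.216: 7.849 × (0.1971 + 0.1693) / 0.002916 = 986 (pooled variance: 990).
- One-sided, pooled: 885 and 779.
- A 20-point absolute change, two-sided: 91 (up) or 55 (down).

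None of these gives 750. Ratios below are therefore applied to 1120, not to 750.

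**Hurdles.**

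- Marascuilo, k = 3: √5.991 = 2.448, a per-pair two-sided alpha of 0.0144.
- Two contrasts only: Bonferroni 2.241; Dunnett-type with equal groups (correlation 0.5) 2.212.
- One contrast: 1.960.

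**Sample-size ratios against one contrast**, from ((c + 0.842) / (1.960 + 0.842))²:

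- Marascuilo, k = 3: 1.379, so 1120 becomes about 1545.
- Bonferroni on two: 1.211, about 1357.
- Dunnett-type on two: 1.188, about 1331.
- Avoidable excess: 1.379 / 1.211 = 1.14 and 1.379 / 1.188 = 1.16.

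**Power for 27% vs 32.4%.** At 750 per group, SE = √(0.1971/750 + 0.2190/750) = 0.02356, so the expected z is 0.054 / 0.02356 = 2.292. Power = Φ(2.292 − c). Other sizes follow in the same way.

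| Per group | Marascuilo (k = 3) | Two contrasts (Bonferroni to Dunnett) | One contrast |
|---|---|---|---|
| 750 | 44% | 52–53% | 63% |
| 1000 | 58% | 66–67% | 75% |
| 2000 | 90% | 93–94% | 96% |
| 4000 | 99.8% | 99.9% | above 99.9% |

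For 27% vs 21.6% at 750 per group, the one-contrast and Marascuilo figures are 68.5% and 49.8%.

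**Error actually spent.** In 400,000 simulated null trials (k = 3, 750 per group, p = 0.27), the chance of any false rejection was 3.9% over all three pairs and 2.8% over the two wanted contrasts.

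**Other values of k.** If the two intervention sites stay separate (k = 4), the hurdle is 2.795, the ratio to one contrast 1.69 and power at 750 per group 31%.

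**The case against.** A reader might infer that the whole 38% is the price of the unwanted control-versus-control pair. The documents do not support this. The 38% is measured against a single unadjusted contrast, whereas section 17 names two comparators. Adjusting for those two alone costs 19–21%.

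A reader might also take the distance from the stated 80% to 44% as the cost of the procedure. It is not. The step from 80% to 63% arises because 750 does not follow from the stated inputs, which is a separate sizing error. So is the conflict in section 13 between an increase and a decrease.

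The strongest defence is the planned sample. At 4000 per group the loss all but vanishes. The ratio of required sample sizes holds at every size, but the loss of power does not. This largely stands, with two limits. The 4000 is a target per site, its split between phases is not stated, and the only firm floor is 1000 in Phase I. The analysed set may also be smaller than enrolment, because the published protocol (Primary outcomes) restricts the endpoint to emergency and priority cases. That fraction is not given. If it were 25% or 50% (assumptions), 4000 enrolled would leave 1000 or 2000 analysed, where Marascuilo gives up about 8–9 or 3 points of power against a two-contrast adjustment.

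Finally, it would go too far to call this the primary-endpoint test. Section 17 labels no analysis as primary, and section 11 names time to the bundle as the outcome, with the 60-minute proportion derived from it. The published protocol names a difference-in-differences logistic model as primary, but version 5.0 (October 2020) is later than that publication (June 2020). The status of the Marascuilo comparison is therefore open. No success rule is given either; if success required beating both controls, no adjustment would be needed.

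**Conclusion.** The point holds as a modest matter of efficiency and consistency. Version 5.0 names an all-pairs procedure for a question with two contrasts, and its sample size is set for one. On the k = 3, equal-groups reading, the avoidable excess is about 14–16% in sample size, or 8–9 points of power at 750 or 1000 per group. The error spent on the two wanted contrasts is about 2.8% instead of 5%. The loss is negligible near 4000 per group and matters only if analysed numbers fall well below target.

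The hurdles and ratios are exact once k is fixed, apart from the Dunnett value, which needs equal groups. The power and error figures also rest on equal groups, and the power figures on the 27% versus 32.4% alternative. Since the documents do not state k, these sizes are conditional; k = 4 would raise the hurdle further.

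**What to change.** In section 17, state which groups enter the 60-minute comparison, including how sites and controls are combined. This needs care because section 8 adds Gulu as a control while the Kenyan sites are delayed. Replace Marascuilo with Holm, or with a Dunnett-type test (critical value about 2.21 with equal groups), on the two intervention-versus-control contrasts. Report the historical-versus-contemporaneous difference descriptively with an interval. In section 13, restate the power for that test.

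If the sponsor can name one contrast as primary, a pre-specified fixed order is an alternative: the first contrast at z = 1.960, and the second tested only if the first succeeds. That recovers the full 1.38 ratio for the first contrast, but makes the second confirmatory only conditionally. Which contrast ranks first is the sponsor's choice.

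The change of test takes about one sentence, plus a short revision of the power paragraph. What is given up is a confirmatory test of control against control.
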